10	Appendix 3: Scoring for Epworth Sleepiness Scale	39
11	Appendix 4: Scoring for Stop Bang Questionnaire	40
12	Appendix 5: Definitions of hypoglycaemia.....	41
13	Appendix 6: IPAQ scoring system.....	43
14	Appendix 7 Definitions for adherence of participants with the LIRA 3mg..	45
14.1	52 weeks	45
14.2	104 weeks	46
15	Appendix 8: Baseline and follow-up Glycaemic Status Definitions	47
15.1	Baseline Glycaemic Status	47
15.2	Follow-up Glycaemic Status	48
16	Appendix 9: Templates for Tables	49
16.1	Disposition.....	49
16.2	Protocol deviations	49
16.3	Summary of continuous baseline characteristics.....	50
16.4	Summary of categorical baseline characteristics.....	52
16.5	Comparison of continuous baseline characteristics between those with and without primary outcome data	54
16.6	Comparison of categorical baseline characteristics between those with and without primary outcome data	56
16.7	Analysis of primary outcome	58
16.8	Analysis of secondary categorical anthropometric outcomes	59
16.9	Analysis of secondary continuous anthropometric outcomes	61
16.10	Summary of other categorical secondary outcomes.....	66
16.11	Summary of other secondary continuous outcomes.....	69
16.12	Summary of categorical safety outcomes.....	79
16.13	Summary of continuous safety outcomes.....	80
16.14	Summary of categorical compliance outcomes.....	83
16.15	Summary of Adverse events by MEDRA and expected adverse event terms	85

1 Introduction

This Statistical Analysis Plan (SAP) describes the planned analysis and reporting for the following study: *Effectiveness and cost of integrating a protocol with use of Liraglutide 3.0mg into an obesity service (STRIVE Study)*. The structure and content of this SAP provides sufficient detail to meet the requirements identified by the FDA and International Conference on Harmonization of Technical Requirements for Registration of Pharmaceuticals for Human Use (ICH): Guidance on Statistical Principles in Clinical Trials. All work planned and reported for this SAP will follow internationally accepted guidelines, published by the American Statistical Association and the Royal Statistical Society for statistical practice.

The reader of this SAP is encouraged also to read the clinical trial protocol.

The purpose of this SAP is to outline the planned analyses that are to be performed on the data to support the completion of the Clinical Study Report (CSR), i.e., this SAP only covers the final analyses. The SAP will be amended if there are substantial changes to the planned analyses, and in any case will be finalized and signed off before the database lock for this study.

Exploratory post-hoc or unplanned analyses not necessarily identified in this SAP may be performed on these data as required. These analyses will be clearly identified in the CSR and in any subsequent publications of the data that include post-hoc or unplanned analyses.

It is planned that health economics analyses will be performed. These will be handled separately and are not described in this SAP.

Interim analyses have not been performed for this study. Safety analyses were conducted for the Data Monitoring Committee reports, but no efficacy analyses took place.

Throughout the document, any verbatim text from the protocol is provided inside a box, i.e.:

Text from the protocol

1.1 Study Objectives

1.1.1 Primary Objectives

The primary objective will be to compare the proportion of participants with severe and complicated obesity (defined as $BMI \geq 35 \text{ kg/m}^2$ with at least one major obesity-related comorbidity) achieving weight loss $\geq 15\%$ at 1 year (52 weeks) with a targeted prescribing pathway (i.e. use of LIRA 3mg according to a pre-specified protocol in combination with standard care provided in Tier 3 services) versus standard care provided in Tier 3 services alone.

1.1.2 Primary Aim

The aim of the study is to compare the effectiveness, budget impact, and cost-effectiveness between two treatment pathways (standard care vs a targeted prescribing pathway plus standard care) in a real-world setting among otherwise largely unselected patients.

The secondary objectives are to compare the targeted prescribing pathway and standard care in terms of:

1. *improving obesity-related co-morbidities (obstructive sleep apnoea, prediabetes, diabetes, hypertension, dyslipidaemia, depression)*
2. *referral rates to other obesity interventions*
3. *long-term maintenance (defined as the proportion of participants maintaining weight loss of $\geq 15\%$ at 104 weeks among those who achieved $\geq 15\%$ weight loss at 52 weeks)*
4. *budget impact on a Tier 3 weight management service*
5. *long-term cost-effectiveness*
6. *direct healthcare costs in terms of admissions, frequency, and cost of appointments*
7. *safety-related outcomes*
8. *adherence*
9. *patient satisfaction.*

1.1.3 Secondary Objectives

Secondary objectives number 4-6 will be dealt with as part of the health economics analysis and are not included in this SAP.

1.1.4 Subgroup Objectives

None

1.2 Study Design

1.2.1 Overview

A 26 month, parallel, two group, open-label, real-world, randomized controlled trial design for patients with severe and complex obesity who are referred to a Tier 3 obesity service (including patients who are referred to a Tier 3 service as part of the bariatric surgery pathway). The total duration of participation will be 104 weeks (+/-2 weeks). Figure 1 shows an overview of the study design.

The first 52 weeks of the study (after randomisation) will determine whether using the

[figure not shown]

targeted prescribing pathway in a Tier 3 setting will result in more participants attaining $\geq 15\%$ weight loss compared with standard care. The purpose of the long-term (52-104 weeks) follow-up is to examine whether LIRA 3mg will help the “early and good” responders to maintain weight loss $\geq 15\%$ in comparison with the control group over a longer period of time compared with standard care. Further, budget impact, cost-effectiveness, improvement in obesity-related co-morbidities, complementary aspects of safety, effectiveness, adherence, and treatment satisfaction of both treatment groups will be assessed and compared.

Participants will be randomised in a 2:1 fashion (2 intervention: 1 control) to either 1) the intervention of targeted prescribing pathway (obesity-specialist care plus targeted use of Liraglutide 3.0mg [LIRA 3mg] with pre-specified stopping rules for the medication) plus standard care, or 2) control (standard care). All participants will be analysed in the group to which they are randomised; in particular, participants in the intervention group who stop receiving LIRA 3mg will remain in the intervention group and will continue to receive standard care for the remainder of the study as per the targeted prescribing pathway (albeit, the part of the pathway where LIRA 3mg is not prescribed; see Figure 1).

The study is intentionally designed to reflect a pragmatic “real-world” scenario and each Tier 3 provider may require a different number of visits for their programme. However, study appointments for data collection, titration reviews, application of the stopping rules of LIRA 3mg, and dispensing were standardised for all of the five sites. Where participants were lost to follow up or missed a study visit, the study team attempted to access data for weight measurements from existing hospital, GP or health records, where appropriate consent was in place, to ensure that the primary outcome was as complete as possible.

FIGURE 1:
Study Design

1.2.2 Participants

Inclusion Criteria

To be considered eligible to participate in this study, a patient must:

- *be aged between 18-75 years old (inclusive)*
- *understand written and spoken English*
- *be able to give informed consent*
- *have a BMI $\geq 35 \text{ kg/m}^2$*
- *have been referred to the Tier 3 service in one of the participating sites*
- *have a stable body weight (less than 5kg self-reported change during the previous 12 weeks)*
- *have at least one of prediabetes, diabetes, hypertension, and/or obstructive sleep apnoea, as defined below:*
 - *prediabetes (defined as established diagnosis of impaired fasting glycaemia (IFG) from GP and/or established diagnosis of impaired glucose tolerance (IGT) from GP and/or HbA1C 42-47 mmol/mol (6-6.4%) without glucose lowering medications, at a blood test during the last 6 months)*
 - *diabetes (defined as established diagnosis of Type 2 diabetes from GP and/or HbA1C $\geq 48 \text{ mmol/mol} (\geq 6.5\%)$ at a blood test during the last 6 months] and/or being treated with any combination of lifestyle, metformin, sulphonylureas, Thiazolidinediones (TZDs) or SGLT-2)*
 - *hypertension treated (defined as being on antihypertensive treatment with or without a diagnosis of hypertension from GP) or untreated (defined as Systolic Blood Pressure $\geq 140 \text{ mmHg}$ at two consecutive visits at the Tier 3 clinic),*
 - *obstructive sleep apnoea (on CPAP or established diagnosis of Apnoea Hypopnoea Index ≥ 15 at sleep studies during the last 12 months).*

Exclusion criteria are stated in the protocol, and cover contradictions to LIRA 3mg and criterion that would be likely to prevent full participation in the study protocol.

1.2.3 Treatment groups

1.2.3.1 Intervention group (Targeted Prescribing Pathway)

The NHS Weight Management pathway is divided into four distinct tiers:

***Tier 1:** health promotion*

***Tier 2:** lifestyle interventions*

***Tier 3:** specialist multidisciplinary weight management services*

Tier 4: bariatric surgery

Across the UK, each region has a specialist Tier 3 obesity and/or weight management service or equivalent, usually referred to as Tier 3. This includes a clinician led multidisciplinary team approach, potentially including a specialist physician, nurse, dietician, psychologist, physiotherapist, etc. From this point forwards, Tier 3 specialist weight management and/or equivalent services will be referred to as 'Tier 3' throughout the remainder of this protocol.

Participants in the intervention group will receive the same standard care as those in the control group, i.e. the best medical practice delivered by the Tier 3 service at each site. Additionally, at baseline, LIRA 3mg will be prescribed to all of the participants in the intervention group at a starting dose of 0.6mg daily. Dose escalation of Liraglutide will occur according to a pre-specified titration protocol, from 0.6mg to a maximum of 3.0mg daily. Liraglutide dose will be initiated at 0.6mg and then increased to 1.2mg in Week 2, 1.8mg in Week 3, 2.4mg in Week 4, and 3.0mg in Week 5. Participants in the intervention group will be aware that the LIRA 3mg treatment may be stopped at various time points throughout the duration of the study and that continued use of LIRA 3mg is based upon their response to the treatment in terms of them achieving pre-defined weight loss targets at 16, 32 and 52 weeks. Specifically, participants in the intervention group will continue to be prescribed LIRA 3mg for the 104 week duration of the study, unless one of the following stopping rules applies:

1st stopping rule

After 16 weeks (\pm 14 days) on the medication, only those participants who have lost $\geq 5\%$ of their baseline weight will be offered further treatment with LIRA 3mg for another 16 weeks. Participants who have not met this weight loss target will have their LIRA 3mg treatment stopped but will still continue in the targeted prescribing pathway but will receive standard care only during the remainder of the study.

2nd stopping rule

After 32 weeks (\pm 14 days) on the medication, only those participants who have lost $\geq 10\%$ of their baseline weight and are still on treatment with LIRA 3mg will be offered another 20 weeks on LIRA 3mg. Participants who have not met this weight loss target will have their LIRA 3mg treatment stopped but will still continue in the targeted prescribing pathway but will receive standard care only during the remainder of the study.

3rd stopping rule

After the first year of treatment (week 52; \pm 14 days), only those participants who have lost $\geq 15\%$ of their baseline weight and are still on treatment with LIRA 3mg will be offered another 52 weeks on LIRA 3mg. Participants who have not met this weight loss target will

have their LIRA 3mg treatment stopped and will still continue in the targeted prescribing pathway but will receive standard care only during the remainder of the study.

Participants who fail to reach the pre-defined weight-loss targets to continue LIRA 3mg treatment, or who choose to stop receiving LIRA 3mg, will continue to be offered the standard care provided by the Tier 3 service. These participants will still attend the Clinical Review Visits but not the additional visits for participants who are still on LIRA 3mg (e.g. Weeks 65 & 91) because these visits will not be relevant to them; visits at Weeks 65 and 91 are intended to provide a new prescription of LIRA 3mg and to discuss adherence and any side effects).

Participants will remain routinely in the Tier 3 service in-line with NICE guidance throughout the duration of the research study. Participants may be offered treatment options within the duration of the study, including bariatric surgery, as per NICE guidance and according to the decision of the local Tier 3 Multidisciplinary Team.

1.2.3.2 Control group (standard care)

Participants in the control group will follow the best medical care provided by the Tier 3 service at the relevant site. This typically involves dietary advice to reduce energy intake (and may include a period of partial or total meal replacement), accompanied – if available – by a physical activity programme, both supported by behavioural change techniques with regular professional contacts. The nature of the standard care will vary between the different Tier 3 services at each site, as this is a pragmatic 'real-world' study. Clinician input will include the medical assessment of participants for severe and complicated obesity and the prescription of anti-obesity drugs (such as Orlistat) as per local Tier 3 service policy. As with the LIRA 3mg group those patients taking antihypertensive or antidepressant medication will be assessed and it will be at the clinician's discretion as to whether these medications are changed. Participants will remain routinely in the Tier 3 service in line with NICE guidance throughout the duration of the research study. Participants may be offered treatment options within the duration of the study, including bariatric surgery, as per NICE guidance and according to the decision of the local Tier 3 Multidisciplinary Team.

1.2.4 Sample size

Based on previous studies, it is expected that at one year approximately 5% of the participants in the standard care group will have achieved $\geq 15\%$ weight loss (likely range: 3%-5%). An achievable target for $\geq 15\%$ weight loss at one year in the intervention group is 16% (likely range: 14%-20%). Based on these proportions, 25% drop out, 5% alpha and a 2:1 randomisation ratio with the higher proportion of participants being randomised to the

intervention group, we would need to recruit 392 participants (261 intervention group; 131 standard care) to have 80% power to detect a significant difference between the groups at one year. With 261 participants randomised to the intervention group, and based on 16% achieving $\geq 15\%$ weight loss at 12 months, an estimated 40 participants in the intervention group will be eligible for the responder analyses. All 131 participants in the standard care group will be eligible for the responder analyses.

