5.4.1 Primary Analysis of Primary Outcome

The primary analysis will compare the proportion of participants achieving $\geq 15\%$ weight loss at 52 weeks (primary outcome) after randomisation between the two randomisation groups. The primary outcome will be summarised using count and percentage. A logistic regression model will be used with a binary indicator showing whether or not $\geq 15\%$ weight loss was achieved at 52 weeks as the outcome, randomisation group (intervention or control) as the main covariate, and the stratification factors of site (non-ordinal categorical variable) and baseline BMI ($\geq 45\text{kg}/\text{m}^2$; $<45\text{kg}/\text{m}^2$) as additional covariates. The adjusted odds ratio will be presented, 95% confidence interval and p-value comparing the two groups.

The primary analysis will use the complete cases population, therefore missing data will not be imputed.

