5.4.3 Sensitivity Analyses

No sensitivity analyses are planned.

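### With 3 to 5 control achievers expected, the primary logistic model leaves its test unnamed, gives an odds ratio that runs modestly high, and has no rule for zero control events

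*SAP*

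**What the plan says.** SAP 1.2.4 (repeating Protocol 11.2) states that "it is expected that at one year approximately 5% of the participants in the standard care group will have achieved" the endpoint, with a likely range of 3% to 5%. It takes 16% (range 14% to 20%) as achievable in the intervention group. "Based on these proportions, 25% drop out, 5% alpha and a 2:1 randomisation ratio", it arrives at "392 participants (261 intervention group; 131 standard care) to have 80% power to detect a significant difference between the groups at one year".

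SAP 5.4.1 fits a logistic regression to complete cases, with randomised group, site and BMI group as covariates: "The adjusted odds ratio will be presented, 95% confidence interval and p-value comparing the two groups". It does not say how the model is estimated, or whether the p-value and interval are Wald or likelihood-ratio. SAP 4.5 leaves the software open, and SAP 4.6 fixes only two-sided testing at 5%.

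SAP 5.4.2 repeats the model in the ITT and per-protocol populations, and SAP 5.4.4 repeats the per-protocol analysis after further exclusions. Under SAP 5.4.3, "No sensitivity analyses are planned", although SAP 4.2 describes the ITT repeat as a sensitivity analysis. SAP 5.8 replaces the adjusted proportions of Protocol 11.1 with raw values, so the adjusted odds ratio is the only modelled comparison of the arms.

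**The concern.** The information about the odds ratio is limited by its smallest cell, and here that is the number of controls who reach 15%. With so few, the maximum-likelihood odds ratio tends to lie too far from 1, and the usual large-sample tests do not hold their nominal size. If no control reaches 15%, the estimate is infinite.

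This is the single primary result. A known upward bias would favour the intervention. The p-value would depend on a software default that nobody chose. If the zero cell occurred, the analyst would have to pick a method after seeing the data in an open-label trial.

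**Working it through.** **Inputs.** From SAP 1.2.4: control rate 5% (3% to 5%), intervention rate 16% (14% to 20%), 131 and 261 randomised, 25% dropout. From SAP 5.4.1: complete cases; covariates arm, site and BMI group. From SAP 1.2.1: five sites.

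**The plan's own figure.** Two-proportion normal formula, two-sided 5%, 80% power, 2:1, no continuity correction:

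- Pooled rate (0.05 + 2 × 0.16)/3 = 0.1233.
- n(control) = [1.96·√(1.5 × 0.1233 × 0.8767) + 0.8416·√(0.05 × 0.95 + 0.16 × 0.84/2)]² / 0.11² = (0.789 + 0.285)² / 0.0121 ≈ 95.4, so 96.
- Total 96 + 192 = 288, and 288/0.75 = 384, within about 2% of the stated 392. With 98 v 196 evaluable, power is 81.2%.

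The sample size is therefore reproduced.

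**Events and parameters.**

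- Evaluable: 131 × 0.75 ≈ 98 and 261 × 0.75 ≈ 196.
- Control achievers: 98 × 0.05 = 4.9; 98 × 0.03 = 2.9. Intervention achievers: 196 × 0.16 = 31.4.
- Parameters: intercept 1 + arm 1 + site 4 + BMI 1 = 7. Events per parameter: (4.9 + 31.4)/7 ≈ 5.2.

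**Chance of no control achiever, (1 − p)^n.**

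- n = 98: 0.95^98 = 0.7%; 0.96^98 = 1.8%; 0.97^98 = 5.0%.
- All 131 controls observed: 0.97^131 = 1.8%.
- 70 controls left in a per-protocol set (an illustrative assumption): 0.95^70 = 2.8%; 0.97^70 = 11.9%.

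**Simulation of the SAP model.** There were 20,000 trials per scenario for maximum likelihood (ML) and for the Firth mean. Runs of 2,000 to 4,000 trials gave the penalised tests, coverage and Firth median. Site sizes, the BMI split and site effects are not in the documents, so they are assumed. The base setting has equal sites and no site or BMI effect (35% at BMI ≥45 in the smaller runs). A second setting, with unequal sites and real site and BMI effects, gave nearly the same bias and test sizes.

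| Quantity | Result |
|---|---|
| True odds ratio, 5% v 16% | (0.16/0.84)/(0.05/0.95) = 3.62 |
| ML, geometric mean of finite fits | 4.05, ratio 1.118 (1.105 to 1.126 across scenarios) |
| ML, median | about 1.02 to 1.09 times truth |
| Firth, geometric mean | 1.00 to 1.01 times truth |
| Firth, median | about 4% to 10% low |
| Wald 95% CI coverage, finite fits | about 97% |
| Size at a common 5% rate | Wald 2.8%, ordinary LR 5.7% |
| Size at a common 3% rate | Wald 2.2%, ordinary LR 6.8% |
| Size, penalised LR | about 3% to 5% |
| Power, 5% v 16% | Wald 81%, penalised LR 82.5% |
| Power, 4% v 14% | Wald 77%, penalised LR 80% |
| Power, 3% v 14% | Wald 85%, penalised LR 91% (83.9% v 90.7% in a second run) |

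Bias against noise at 5% v 16%: ln(1.11) = 0.10 and ln(1.118) = 0.11, with a mean standard error of about 0.54. The ratio is 0.19 to 0.21, or about one-fifth of a standard error.

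Most of the power gap at 3% comes from the zero cell. A Wald test on a diverging fit does not reject, and those trials are 5% of the total.

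**The case against.** The strongest reply is that little harm follows. The bias is about one-fifth of a standard error, the Wald interval covers about 97%, and a conservative test is not an invalid one. This stands, and it rules out reading the point as a misleading primary result.

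Three other replies also stand in part:

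- **The 11% depends on the scale.** It is a log-scale mean over finite fits. On the median, ML errs high by about 2% to 9% and Firth errs low by about 4% to 10%, so Firth is not better on every measure.
- **The Wald test is assumed.** It is the usual software default, but the SAP does not name it. A reader might infer that the plan commits to a conservative test. It does not, and an ordinary likelihood-ratio test would err the other way. What the text supports is that the p-value is not fully specified.
- **The zero cell is rare at the planning value.** It is 0.7% at 5%. The 5% figure needs the lowest stated control rate and the full dropout. Routine-record weights and the wider visit window (SAP 1.3) should reduce the loss. Exclusion after bariatric surgery (SAP 3.3.1), which Protocol 6.2 expects more often in controls, works the other way. If the cell were empty, table 16.7 in SAP Appendix 9 would still show counts and percentages by arm.

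A reader might also take SAP 5.4.3 to mean that no supporting analysis exists. That is too strong: ITT and per-protocol repeats are planned. But they use the same model. The ITT rule codes missing outcomes as failures, so it adds no control achievers except possibly surgery participants. The per-protocol set is smaller. Neither repeat is a fallback for sparse data.

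**Conclusion.** The point holds as a modest, inexpensive improvement to the primary analysis. On the plan's own rates the model has about 5 control achievers (about 3 at the low end) for 7 parameters. The ordinary odds ratio is then about 11% high on the log-mean scale among finite fits, the size of the test depends on an unstated choice, and a 0.7% to 5% chance of no finite estimate is not provided for.

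It would be wrong to conclude that the trial is underpowered. The sample size is reproduced and 80% power is met at 5% v 16% even with a Wald test. The avoidable loss is 1.5 points there, and about 6 to 7 points at 3% v 14%.

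The event counts and zero-cell probabilities depend only on the SAP's figures and on 98 evaluable controls. The bias, size and power figures also depend on the assumed site and BMI distributions.

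**What to change.** In SAP 5.4.1, keep the model and covariates and add one sentence: the model is estimated by Firth penalised likelihood, with the 95% CI and p-value from the penalised profile likelihood. Apply the same method in 5.4.2 and 5.4.4, where the control cell may be smaller still. Report the ordinary maximum-likelihood odds ratio alongside.

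This always gives a finite estimate, keeps test size at or somewhat below nominal, settles which test is used, and loses no power in the scenarios examined.

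The cost is one SAP sentence and one software option. The SAP is marked version 1.1 draft, and its introduction says it will be signed off before database lock, so the change fits its own timetable. The downside is that the reported odds ratio will be about 10% smaller than the ordinary one (1.007/1.118 = 0.90 at 5% v 16%), and its median slightly low.
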